5.5.2 Dispensing the study drug

Each study site will be supplied with study drug in packaging of identical appearance.

The study drug packaging has a 2-part label. A unique medication number is printed on each part of this label which corresponds to one of the 2 treatment arms. Investigator staff will identify the study drug package(s) to dispense to the patient by contacting the IRT and obtaining the medication number(s). Immediately before dispensing the package to the patient, investigator staff will detach the outer part of the label from the packaging and affix it to the source document (Drug Label Form) for that patient's unique subject number.

5.5.3 Handling of study and additional treatment

5.5.3.1 Handling of study treatment

Study treatment must be received by a designated person at the study site, handled and stored safely and properly, and kept in a secured location to which only the investigator and designees have access. Upon receipt, all study treatment must be stored according to the instructions specified on the labels. Clinical supplies are to be dispensed only in accordance with the protocol. Technical complaints are to be reported to the respective Novartis CPO Quality Assurance.

Medication labels will comply with the legal requirements and be printed in German. They will include storage conditions for the study treatment but no information about the patient except for the medication number.

The investigator must maintain an accurate record of the shipment and dispensing of study treatment in a drug accountability log. Monitoring of drug accountability will be performed by monitors during site visits or remotely and at the completion of the trial. Patients will be asked to return all unused study treatment and packaging for every study visit and at the end of the study or at the time of discontinuation of study treatment.

At the conclusion of the study, and as appropriate during the course of the study, the investigator, supported by the Novartis monitoring team, will return all unused study treatment, packaging, drug labels, and a copy of the completed drug accountability log to the Novartis address provided in the investigator folder at each site.

5.5.3.2 Handling of additional treatment

Not applicable.

5.5.4 Instructions for prescribing and taking study treatment

The investigational product dose is either 70 mg or 140 mg depending on the investigators decision, which has to be made for each patient individually and in accordance with the product information: the recommended dose is 70 mg, some patients may benefit from 140 mg (see Section 5.1 of AIMOVIG® SmpC).

In case of insufficient response, the dose may be escalated from 70 mg to 140 mg. Possible reasons for up titration could be, but are not limited to:

- insufficient response as deemed by physician and/or patient
- reduction of acute medication use not satisfactory
- insufficient improvement in life quality

An adjustment of the 70 mg dose to 140 mg can be performed at any time during the DBTE. The investigational product dose of 140 mg must not be changed once a patient received the dose during DBTE.

Reference treatment doses are determined during the uptitration phase and must aim to reach the recommended daily treatment dose of 100 mg topiramate in accordance to the German SmPC. The reference treatment dose established during the up titration phase must not be changed during the 18-week maintenance phase.

There are no temporal restrictions for the investigational or the reference treatment (e.g., proximity to meals, sleep or activity).

Test-IMP:

70 mg and 140 mg erenumab or respective placebos will be administered by qualified study staff at each dosing visit during the 24 week double-blind treatment epoch (i.e., at Day 1 and Week 4, Week 8, Week 12, Week 16 and Week 20). Subcutaneous (s.c.) injections are to be given for each investigational product administration. For purposes of study treatment dosing, “q.m.” refers to an every 4 weeks injection regimen. The study drug administration date should be in 4 week increments (+/- 4 days) from the first dose of study drug. Any dose administrations that may occur greater than +/- 4 days from the 4 week time point (e.g., patient unavailability) should be discussed with the Sponsor prior to dosing. The anatomical sites for administration of investigational product are the upper arm, upper thigh, or abdomen; the location of the injection site should be documented in the source document. In order to reduce irritation at the injection site, the investigational product should be stored at room temperature for 30 minutes prior to the administration.

Control-IMP:

Topiramate and oral placebo will be administered by the patient himself. During the first week of the titration phase topiramate 25 mg or matching placebo will be administered once daily. After the first week, topiramate titration will be done according to the SmPC in 25 mg increments each week and must aim to reach the recommended daily treatment dose of 100 mg (50/75/100 mg). Topiramate 50/75/100 mg or matching placebo will be administered twice daily during titration phase and maintenance phase. The physician may decide to allow the patient to remain on this dose for another week if there are tolerability concerns. If a patient is not deemed suitable for uptitration during the 6 weeks titration period, the patient may remain on highest tolerated dose throughout the trial. Minimal dose to enter maintenance phase has to be 50 mg, patients not tolerating 50 mg topiramate have to be taken off prophylactic study treatment, but maintain in study on supportive care. Maximal dose for topiramate is 100 mg.

Downtitration is not allowed in this trial. Patients who discontinue study treatment or complete the study with a daily dose of 75 mg or 100 mg topiramate should taper off topiramate for one week with a daily dose of topiramate reduced by 50 mg.

Titration phase (week 1 till end of week 6) (according to current topiramate product information)

Titration of topiramate has to be made in 25 mg increments each week and must aim to reach the recommended migraine treatment dose of 100 mg in accordance to the SmPC. If a patient initially cannot tolerate the next dose step, he may stay on the current dose for another week. However, at the end of the 6 week titration phase, patients must reach at least the 50 mg topiramate dose to maintain in the DBTE.

Exemplatory titration scheme:

Week 1: 25 mg topiramate (= 1x 25 mg /day in the evening)

Week 2 : If patient tolerates 25 mg topiramate--> uptitration to 50 mg topiramate (2x 25 mg/day)

Week 3: If patient tolerates 50 mg topiramate --> uptitration to 75 mg topiramate (25 mg and 50 mg, each 1x/day) (=75 mg topiramate/day)

Week 4: If patient tolerates 75 mg --> uptitration to 100 mg topiramate (2x 50 mg/day)

Week 5 and 6: further uptitration to next dose for patients who had to prolong titration during weeks 1 – 4 due to initial poor tolerability.

Starting with week 7, patient has to take a stable dose (50 mg, 75 mg or 100 mg topiramate).

Patients who are not able to tolerate 50 mg have to be discontinued from drug, but should remain in the trial for documentation purposes. During this time, patients may use treatments described under 5.5.6 for their acute migraine attacks.

Maintenance phase (start of week 7 to end of week 24):

Control-IMP doses are determined during the uptitration phase and must not be changed during the 18-week maintenance phase. Patients have to remain on their highest tolerated dose (50 mg, 75 mg or 100 mg topiramate) throughout maintenance phase. If a patient cannot tolerate dose during maintenance phase, he/she has to be discontinued from all study treatment, but should remain in the trial. This patient is allowed to continue using rescue medication as described under 5.5.6.

All kits of study treatment assigned will be recorded in the IRT. Novartis monitors will reconcile treatment assigned vs treatment administered and ensure that the information is congruent during their monitoring visits.

Tapering off

Control-IMP should be tapered off by patients who complete the study (Visit 199, end of week 24) or discontinue study treatment after receiving a daily dose of 75 mg or 100 mg Control-IMP. Tapering off is performed by reducing the daily dose of Control-IMP by 50 mg for one week before a patient stops taking the drug.

Exemplatory Tapering off scheme:

Patient on 100 mg/day topiramate --> One week 50 mg/day topiramate --> No more medication

Patient on 75 mg/day topiramate --> One week 25 mg/day topiramate --> No more medication

Patient on 50 mg/day topiramate --> No more medication (no tapering off required)

Patient on 25 mg/day topiramate --> No more medication (no tapering off required)

5.5.5 Permitted dose adjustments and interruptions of study treatment

Control-IMP dose adjustments are allowed during the 6-week up titration phase only and must be kept stable during the 18-week maintenance phase. Investigational treatment dose adjustments from 70 mg to 140 mg can be made throughout the whole trial. Titration for topiramate and for erenumab 70 mg to 140 mg can be done independently. Interruptions are allowed as specified in Section 5.5.9. Additionally, investigator-initiated interruptions will be considered on a case-by-case basis.

5.5.6 Rescue treatments

Patients can continue to use acute migraine medication and non-pharmacological interventions as rescue treatments. These may include both pharmacologic interventions (i.e., treatments for acute attacks such as triptans and NSAID) and non-pharmacologic treatments (e.g., biofeedback, psychotherapy or other locally accepted and endorsed interventions for migraine). Non-pharmacological treatment options may only be used as rescue therapy, if patient has been stable on the specific non-pharmacological treatment 3 months prior to baseline.

Patients discontinued from study drug may only use rescue treatments for their migraine attacks as described above.

Site staff will pre-specify the name, dose strength, and route of administration of the patient's acute headache (rescue) medications in the patient's eDiary. If the patient takes an acute headache medication during aura or to treat a migraine or non-migraine headache, they will select one of the pre-specified medications (or "other" medication) and enter the date of administration, the number of times the medication was taken on that date and number of units taken.

Use of rescue medication must be recorded in the eDiary. The acute headache medications reported in the eDiary also will be collected on the Concomitant medications/Significant non-drug therapies eCRF, but data will include only the drug name, indication, and start and stop dates of overall use (i.e., not the individual administration dates). Relevant non-drug therapies as part of "best supportive care" use should also be recorded in the eCRF.

5.5.7 Concomitant medication

The investigator must instruct the patient to notify the study site about any new medications he/she takes after enrolling into the study. All medications, procedures and significant non-drug therapies (including physical therapy and blood transfusions) administered after the patient was enrolled into the study must be recorded in the concomitant medications/ significant non-drug therapies eCRF.

Each concomitant drug must be individually assessed against all exclusion criteria/prohibited medication. Potential interactions of each concomitant drug with topiramate, according to SmPC section 4.5, must be individually assessed as additional clinical monitoring of defined parameters might be necessary (e.g., adequate control of diabetic disease state). If in doubt the investigator should contact the Novartis medical monitor before randomizing a patient or allowing a new medication to be started.

5.5.8 Prohibited treatments

Use of the treatments displayed in Table 5-1 is NOT allowed as designated due to the potential confounding of efficacy assessments unless in the context of a different pre-existing condition in stable doses for at least 3 months prior to baseline.

Table 5-1 Prohibited Treatments

Treatment	Prohibition period
All prophylactic treatments targeting the CGRP pathway	Any time before study start and throughout the study
Topiramate	Any time before study start
Valproate/Divalproex	Any time before study start and throughout the study
All oral beta blockers	Within 5 half-lives of the start of the baseline epoch and throughout the study
Flunarizine	
Antidepressants (amitriptyline, venlafaxine, desvenlafaxine)	
Antiepileptics (e.g. gabapentin)	
ACE/ARB (lisinopril, candesartan)	
Botulinum toxin (in the head and/or neck region) for medical treatment	Any time before study start and throughout the study
Botulinum toxin (in the head and/or neck region) for cosmetic treatment	Within 4 months of the start of the baseline epoch and throughout the study
Invasive interventions (e.g., nerve blocks, occipital nerve stimulators, transcranial magnetic stimulation)	Within 1 month of the start of the baseline epoch and throughout the study

5.5.9 Emergency breaking of assigned treatment code

Emergency code breaks must only be undertaken when it is required in order to treat the patient safely. Most often, study treatment discontinuation and knowledge of the possible treatment assignments are sufficient to treat a study patient who presents with an emergency condition. Emergency treatment code breaks are performed using the IRT. When the investigator contacts the system to break a treatment code for a patient, he/she must provide the requested patient identifying information and confirm the necessity to break the treatment code for the patient. The investigator will then receive details of the investigational drug treatment for the specified patient and a fax or e-mail confirming this information. The system will automatically inform the Novartis monitor for the site and the study team that the code has been broken.

It is the investigator's responsibility to ensure that there is a dependable procedure in place to allow access to the IRT at any time in case of emergency. The investigator will provide:

- protocol number
- study drug name (if available)

- patient number

In addition, oral and written information to the patient must be provided on how to contact his/her backup in cases of emergency, or when he/she is unavailable, to ensure that unblinding can be performed at any time. If a code break occurs, the patient has to discontinue the study.

5.6 Study completion and discontinuation

5.6.1 Study completion and post-study treatment

A patient will be considered to have completed the double-blind treatment epoch when the patient has completed Visit 199 in the protocol.

The patient's completion status will be recorded on the appropriate Study Phase Completion eCRF pages.

For all patients tapering off Control-IMP after study completion, an unscheduled visit has to be conducted after finishing the tapering off phase. At this visit, information about Control-IMP compliance, AEs, SAEs and concomitant medications have to be collected.

For all patients a safety follow-up visit (visit 201) should be conducted 4 weeks after the last visit or 8 weeks after the last IMP injection. The information to be collected at this follow up visit is outlined in Table 6-1.

5.6.2 Discontinuation of study treatment

Discontinuation of study treatment for a patient occurs when study drug is stopped earlier than the protocol planned duration, and can be initiated by either the patient or the investigator.

The investigator must discontinue study treatment for a given patient if, on balance, he/she believes that continuation would negatively impact the risk/benefit of trial participation.

Study treatment must be discontinued under the following circumstances:

- Patient wish
- Pregnancy (see Section 6.5.6 and Section 7.5)
- Use of prohibited treatment as per recommendations in Table 5-1
- Any situation in which study treatment might result in a safety risk to the patient
- Any laboratory abnormalities that in the judgment of the investigator, taking into consideration the patient's overall status, prevents the patient from continuing participation in the study

If discontinuation of study treatment occurs, the patient should NOT be considered withdrawn from the study, and should continue recording in the eDiary as per protocol. Also, patients who discontinued treatment from the double-blind treatment epoch will follow the abbreviated visit schedule until the follow up visit (week 28) is reached (Table 6-2). These visits should be performed with all assessments outlined in Table 6-2. At a minimum, the following data should be collected at clinic visits or via telephone visits:

- new/concomitant treatments
- adverse events / serious adverse events

If the patient cannot or is unwilling to attend any visit(s), the site staff should maintain regular telephone contact with the patient, or with a person pre-designated by the patient. This telephone contact should preferably be done according to the study visit schedule.

Patients who prematurely discontinue the study for any reason should be scheduled for a visit as soon as possible, at which time all of the assessments listed for the final visit (Visit 199) will be performed. At this final visit, the adverse event and concomitant medications should be reconciled on the eCRF. Patients will return for a follow-up visit approximately 8 weeks after their last dose of study medication, and perform the study procedures outlined in Table 6-1.

The investigator must also contact the IRT to register the patient's discontinuation from study treatment. If study drug discontinuation occurs because treatment code has been broken, please refer to Section 5.5.9. Patients who are prematurely withdrawn from the study will not be replaced by an equal number of newly enrolled patients. All patients receiving a daily dose of 75 mg or 100 mg topiramate (for at least one week) should perform a taper off phase for one week after discontinuation of study treatment. After the taper off phase an unscheduled visit should be performed to record control-IMP compliance, AEs, SAEs and concomitant medications.

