3.1 Study design

This study uses a single-cohort, 2-treatment arm, parallel-group randomized, double-blind, double-dummy design in adult patients with episodic migraine and chronic migraine, who must be either naïve or not suitable for or could have failed up to three prophylactic treatments out of: propranolol/ metoprolol, amitriptyline, flunarizine. Patients will be stratified into groups according to their number of migraine days during the baseline epoch.

The following epochs are included in the study design:

- **Screening Epoch (0 – 2 weeks)** – Required for all patients to assess initial eligibility.
- **Baseline Epoch (4 weeks)** – All patients fulfilling eligibility criteria successfully completing the Screening Epoch are invited to participate. Eligibility for randomization will be assessed based on migraine frequency and diary compliance during this epoch.
- **Double-blind, double-dummy Treatment Epoch (DBTE, 24 weeks)** – All patients completing the Baseline Epoch and fulfilling baseline eligibility criteria are invited to participate. Eligible patients will be randomized to one of two treatment arms. Double-blind treatment epoch will start with a titration phase for topiramate of a maximum of 6 weeks to determine the maximal tolerated dose and must aim to reach the recommended treatment dose of 100 mg according to the German SmPC. After the titration phase, maintenance phase will start (18 weeks). Topiramate dose has to be maintained until the end of the DBTE. Erenumab dose at beginning of the DBTE is determined patient-individually by the investigator based on the guidance provided in the SmPC and can be either 70 mg or 140 mg. Dose escalation from 70 mg to 140 mg in case of insufficient response could be considered at any time during the DBTE (see 5.5.4).

[figure not shown]
Dose reduction of topiramate and erenumab is not allowed during DBTE (Visit 101-199). After visit 199 or if the patient discontinues study drug, a one week double-blind taper off phase will follow to ensure proper down titration for topiramate.

At the end of the DBTE (24 weeks) the final assessment to address the objectives will occur.

Follow-Up Epoch (4 weeks) – A Follow-Up Visit 4 weeks after last study visit (or 8 weeks after last IMP injection for discontinued patients) will be required as part of routine safety monitoring. The primary analysis will be triggered when all patients have completed their respective last visit of the double-blind treatment epoch.

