Appendix 2: Liver event and Laboratory trigger Definitions and Follow-up Requirements

Table 13-1 Liver Event and Laboratory Trigger Definitions

	Definition/ threshold
LIVER LABORATORY TRIGGERS	
 • $3 \times \text{ULN} < \text{ALT/AST} \leq 5 \times \text{ULN}$ • $1.5 \times \text{ULN} < \text{TBL} \leq 2 \times \text{ULN}$
LIVER EVENTS	
 • $\text{ALT or AST} > 5 \times \text{ULN}$ • $\text{ALP} > 2 \times \text{ULN}$ (in the absence of known bone pathology) • $\text{TBL} > 2 \times \text{ULN}$ (in the absence of known Gilbert syndrome) • $\text{ALT or AST} > 3 \times \text{ULN}$ and $\text{INR} > 1.5$ • Potential Hy's Law cases (defined as $\text{ALT or AST} > 3 \times \text{ULN}$ and $\text{TBL} > 2 \times \text{ULN}$ [mainly conjugated fraction] without notable increase in ALP to $> 2 \times \text{ULN}$) • Any clinical event of jaundice (or equivalent term) • $\text{ALT or AST} > 3 \times \text{ULN}$ accompanied by (general) malaise, fatigue, abdominal pain, nausea, or vomiting, or rash with eosinophilia • Any adverse event potentially indicative of a liver toxicity*

*These events cover the following: hepatic failure, fibrosis and cirrhosis, and other liver damage-related conditions; the non-infectious hepatitis; the benign, malignant and unspecified liver neoplasms

Table 13-2 Follow Up Requirements for Liver Events and Laboratory Triggers

Criteria	Actions required	Follow-up monitoring
Potential Hy's Law case ^a	
 • Discontinue the study treatment immediately • Hospitalize, if clinically appropriate • Establish causality • Complete liver CRF 	ALT, AST, TBL, Alb, PT/INR, ALP and γ GT until resolution ^c (frequency at investigator discretion)
ALT or AST		
$> 8 \times \text{ULN}$	
 • Discontinue the study treatment immediately • Hospitalize if clinically appropriate • Establish causality • Complete liver CRF 	ALT, AST, TBL, Alb, PT/INR, ALP and γ GT until resolution ^c (frequency at investigator discretion)
$> 3 \times \text{ULN}$ and $\text{INR} > 1.5$	
 • Discontinue the study treatment immediately • Hospitalize, if clinically appropriate • Establish causality • Complete liver CRF 	ALT, AST, TBL, Alb, PT/INR, ALP and γ GT until resolution ^c (frequency at investigator discretion)

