> 5 to $\leq 8 \times \text{ULN}$	
 • Repeat LFT within 48 hours • If elevation persists, continue follow-up monitoring • If elevation persists for more than 2 weeks, discontinue the study drug • Establish causality 	ALT, AST, TBL, Alb, PT/INR, ALP and γ GT until resolution ^c (frequency at investigator discretion)

Criteria	Actions required	Follow-up monitoring
	
 Complete liver CRF 	
> 3 × ULN accompanied by symptoms ^b	
 Discontinue the study treatment immediately Hospitalize if clinically appropriate Establish causality Complete liver CRF 	ALT, AST, TBL, Alb, PT/INR, ALP and γGT until resolution ^c (frequency at investigator discretion)
> 3 to ≤ 5 × ULN (patient is asymptomatic)	
 Repeat LFT within the next week If elevation is confirmed, initiate close observation of the patient 	Investigator discretion Monitor LFT within 1 to 4 weeks
ALP (isolated)		
> 2 × ULN (in the absence of known bone pathology)	
 Repeat LFT within 48 hours If elevation persists, establish causality Complete liver CRF 	Investigator discretion Monitor LFT within 1 to 4 weeks or at next visit
TBL (isolated)		
> 2 × ULN (in the absence of known Gilbert syndrome)	
 Repeat LFT within 48 hours If elevation persists, discontinue the study drug immediately Hospitalize if clinically appropriate Establish causality Complete liver CRF 	ALT, AST, TBL, Alb, PT/INR, ALP and γGT until resolution ^c (frequency at investigator discretion) Test for hemolysis (e.g., reticulocytes, haptoglobin, unconjugated [indirect] bilirubin)
> 1.5 to ≤ 2 × ULN (patient is asymptomatic)	
 Repeat LFT within the next week If elevation is confirmed, initiate close observation of the patient 	Investigator discretion Monitor LFT within 1 to 4 weeks or at next visit
Jaundice	
 Discontinue the study treatment immediately Hospitalize the patient Establish causality Complete liver CRF 	ALT, AST, TBL, Alb, PT/INR, ALP and γGT until resolution ^c (frequency at investigator discretion)
Any AE potentially indicative of a liver toxicity*	
 Consider study treatment interruption or discontinuation Hospitalization if clinically appropriate Establish causality Complete liver CRF 	Investigator discretion

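### The immediate-stop liver rows in Table 13-2 are not reconciled with the one-week taper at 75 or 100 mg, and the taper trigger differs between sections

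*Protocol*

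**What the plan says.** **Liver rules.** Table 13-2 orders "Discontinue the study treatment immediately" for a potential Hy's Law case, ALT or AST above 8 x ULN, ALT or AST above 3 x ULN with INR above 1.5, ALT or AST above 3 x ULN with symptoms, and jaundice. For isolated total bilirubin above 2 x ULN it asks for a repeat test and then says "If elevation persists, discontinue the study drug immediately". Other rows are weaker. For ALT or AST above 5 and up to 8 x ULN the text is "If elevation persists for more than 2 weeks, discontinue the study drug", and for an adverse event suggestive of liver toxicity it is "Consider study treatment interruption or discontinuation".

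**Taper rules.** Protocol section 3.1 says that "if the patient discontinues study drug, a one week double-blind taper off phase will follow". Section 5.1.1 applies the taper to patients on 75 or 100 mg/day, at a daily dose 50 mg lower for one week. Section 5.5.4 applies it to those who complete or who "discontinue study treatment after receiving a daily dose of 75 mg or 100 mg Control-IMP", and its scheme exempts 50 and 25 mg/day. Section 5.6.2 says "All patients receiving a daily dose of 75 mg or 100 mg topiramate (for at least one week) should perform a taper off phase".

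**Order of events.** Section 5.5.4 describes the reduced week as coming ahead of the patient's last tablet. Section 5.6.2 describes it as following discontinuation. The SAP (2.1.1, tablet dose level in the titration phase) likewise treats taper doses as falling after the discontinuation date.

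**The concern.** A patient on 100 mg/day who meets one of the immediate-stop rows falls under two written instructions. Table 13-2 says study treatment ends at once. The taper text says tablets continue at 50 mg/day for a further week. Neither refers to the other, and no section ranks them.

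What is at stake is patient safety. Under one reading, tablets that may contain topiramate continue for a week after a possible serious liver signal. Under the other, a taper that Amendment 1 introduced for safety is left out. Sites may reasonably decide differently.

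The differing trigger is a separate, smaller problem. It can arise during titration, when patients spend their first days at 75 mg and decisions about tolerability are being made.

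**Working it through.** The documents state no figure on this point, so there is none to reproduce. The check sets the texts side by side and uses only simple arithmetic.

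**1. How many liver-event rows carry an immediate order?** Table 13-2 has nine rows for liver events, leaving aside the two laboratory-trigger rows (ALT/AST above 3 to 5 x ULN and bilirubin above 1.5 to 2 x ULN, both asymptomatic).

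| Order | Rows | Count |
|---|---|---|
| Immediate, unconditional | Potential Hy's Law; ALT/AST > 8 x ULN; > 3 x ULN with INR > 1.5; > 3 x ULN with symptoms; jaundice | 5 |
| Immediate if the elevation persists | Isolated bilirubin > 2 x ULN | 1 |
| No immediate order | ALT/AST > 5 to 8 x ULN; isolated ALP; AE suggestive of liver toxicity | 3 |

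5 + 1 + 3 = 9. The conflict is confined to the first six.

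**2. What does the taper add?** The taper dose is the current dose minus 50 mg/day, taken for 7 days.

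| Dose at stop | Taper dose | Tablet days if the immediate stop covers tablets | Tablet days under the taper rule |
|---|---|---|---|
| 100 mg/day | 100 − 50 = 50 mg/day | 0 | 7 |
| 75 mg/day | 75 − 50 = 25 mg/day | 0 | 7 |
| 50 or 25 mg/day | none (5.5.4) | 0 | 0 |

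The two rules part only at 75 and 100 mg/day.

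**3. Are taper tablets study treatment?** The protocol points both ways.

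- *Yes:* the glossary counts as study treatment any drug given as part of required study procedures, and defines treatment discontinuation as a permanent end to taking it. Section 5.1.1 lists the taper under the Control-IMP. Section 5.5.4 places the stop after the taper week. On this reading a taper is incompatible with an immediate stop.
- *No:* section 5.6.2 and the SAP date the taper after discontinuation. On this reading treatment can be discontinued at once with a taper to follow.

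No text says which reading applies when Table 13-2 requires an immediate stop.

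**4. Who tapers?**

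| Section | Dose limit | Minimum time at the dose | Force |
|---|---|---|---|
| 3.1 | none stated | none stated | will |
| 5.1.1 | 75 or 100 mg | none stated | should |
| 5.5.4 | 75 or 100 mg | none stated | should |
| 5.6.2 | 75 or 100 mg | one week | should |

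Take a patient who stops after three days on 75 mg. Sections 5.1.1 and 5.5.4 call for a taper, as does 3.1. Section 5.6.2 does not, because the one-week condition is not met. Under the example titration scheme in 5.5.4, 75 mg begins in week 3, so this can happen on the normal schedule. Section 3.1's lack of a dose limit matters less. Section 5.5.4 says 50 and 25 mg need no taper, and at 50 mg a 50 mg reduction leaves nothing to take.

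**5. Does it reach the analysis?** The SAP takes AE-related discontinuation from a flag on the Treatment Completion eCRF page, so taking or omitting the taper does not change event status. The last tablet date and tablet exposure are each defined with and without the taper, and adverse events are analysed through the end of study.

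**The case against.** The strongest reply is that sites can work with this text. Most taper wording is *should*, and only the design overview in 3.1 is firmer. A specific liver order would naturally outrank a general recommendation, and 5.6.2 obliges the investigator to stop treatment when continuing would worsen the balance of risk and benefit. Section 7.3 also softens discontinuation for liver events to cases where it is appropriate. Much of this stands: the text is ambiguous rather than impossible to follow. But precedence is an inference, since no section states it, and 7.3 sends the reader to Table 13-2 for detail.

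Several stronger readings are tempting, and the documents do not support them.

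- *Every liver event conflicts with the taper.* Only six of the nine rows carry an immediate order, one of them conditional on persistence.
- *Every patient who stops must taper.* Sections 5.1.1, 5.5.4 and 5.6.2 limit the taper to 75 and 100 mg, 5.6.2 adds a time condition, and all three use *should*.
- *Pregnancy and general safety stops contradict the taper in the same way.* Section 5.6.2 makes these stops mandatory but does not call them immediate, and the same list includes the patient's own wish. A stop followed by a taper satisfies that wording. Whether the taper applies there is unaddressed, which is not a contradiction.
- *Blinding creates the conflict.* An unblinded topiramate patient would face the same two instructions, and section 5.5.9 allows a code break when safe treatment requires one. Blinding does bear on the wording: a rule written for patients receiving topiramate names a group that a blinded site cannot identify.
- *The short-stay patient gets opposite orders.* Section 5.6.2 is silent on stays under a week and does not forbid a taper. The sections differ, but they are not opposed.

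**Conclusion.** The point holds as an internal inconsistency in clinical instructions. For five liver criteria, and for isolated bilirubin above 2 x ULN that persists, the protocol orders an immediate stop. For the same patients, if they are on 75 or 100 mg/day, it also provides a week of reduced-dose tablets. It does not say whether the second is compatible with the first. The gap is 0 versus 7 days of tablets at 50 or 25 mg/day. The documents give no incidence for these criteria, so the number of patients affected cannot be stated.

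Separately, the taper trigger is not the same in the four protocol sections that give it.

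A reader might infer that the trial's main result is exposed. It is not: the primary endpoint does not depend on whether the taper is taken, and the SAP already separates tablet dates and exposure with and without it. The reason to act is patient safety and consistent conduct across sites. The conclusion rests on the text of the two documents alone; a site manual that settled precedence would narrow it.

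**What to change.** Reconcile protocol sections 3.1, 5.1.1, 5.5.4 and 5.6.2 with Table 13-2.

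1. State, for example in a footnote to Table 13-2, which instruction governs the tablets when a row requires an immediate stop. Which one prevails is the sponsor's medical decision and is not proposed here.
2. Say once whether taper tablets count as study treatment and whether the taper comes before or after the discontinuation date. Align 5.5.4, 5.6.2 and the SAP with that statement.
3. Use one identical taper trigger (dose and minimum time) in all four sections, worded for Control-IMP so that a blinded site can apply it. Part of 5.5.4 already uses that term.
4. Optionally, clarify in the same edit whether the taper applies to the mandatory stops in 5.6.2 that are not worded as immediate, such as pregnancy.

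The cost is a sentence in each affected section and one table footnote, by amendment or site letter. No new procedure or data collection is needed, and the primary analysis does not change.
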